11.4 Analysis of the primary variable(s)

The primary aim of this study is to assess the efficacy of LYS006 versus placebo on inflammatory facial lesion counts in patients with moderate to severe inflammatory acne. Therefore, a statistical analysis will be performed on the log transformed inflammatory facial lesion count after 12 weeks. The primary analyses will be based on on-treatment data. Data recorded after a patient discontinues study treatment will not be included in the primary analyses. Commercially Confidential Information

11.4.1 **Primary Variable(s)**

The primary variable is the natural log transformed total inflammatory facial lesion counts (sum of papules, pustules, and nodules) at Week 12.

11.4.2 Statistical model, hypothesis, and method of analysis

Data up to Week 12 will be included in a Bayesian mixed effect model for repeated measures (MMRM) for the comparison of LYS006 high dose group versus placebo group at 12 weeks, which is of primary interest. Data from the LYS006 low dose group will also be included in this primary model at the time of IA and later analyses, but will mainly be summarized as described in Section 11.6.

The natural log transformed inflammatory facial lesion count is expected to be approximately normally distributed. It will be analyzed using a Bayesian mixed effect model for repeated measures (MMRM) using Proc MCMC in SAS software (Chen 2011). Baseline adjustment will be implemented by including the log transformed baseline inflammatory facial lesion count in the model as a continuous covariate. The model will also include treatment group, visit, treatment group by visit interaction, log transformed baseline inflammatory facial lesion count by visit interaction and type of center Commercially Confidential Information

as fixed effects. Non-informative priors will be utilized for the fixed effects and for the covariance. An unstructured covariance will be assumed; other covariance structures will be investigated if there is a convergence issue. As supportive analyses, other factors such as gender, race, center and assessor may also be considered in the primary analysis model either as a fixed effect or as a sub-group analyses variable to investigate for potential heterogeneity. The log transformed baseline inflammatory facial lesion count will be centered and standardized prior to being included in the model.

Bayesian posterior probabilities will be used to assess the following PoC criteria as a guidance for decision making (Fisch et al 2015), though other criteria may be taken into account:

Efficacy criteria (only for primary objective) at IA and at the final analysis:

- If there is at least 90% probability that the treatment effect of LYS006 at 12 weeks is better than placebo, i.e., Prob (y_LYS006 y_placebo < 0) > 90%, and
- If there at least 50% probability that the treatment effect at 12 weeks is at least 25% in favor of LYS006, i.e., Prob (y_LYS006 y_placebo < 0.288) > 50%.

where y is the log transformed facial inflammatory lesion count.

The posterior estimates of the treatment effect and the treatment difference (along with its 90% credible interval) at each post baseline visit (with Week 12 being of primary interest) will be provided. The results will be reported in terms of adjusted absolute and percent changes from baseline by back-transforming the estimates from the log-scale. The absolute change from baseline and the percentage change from baseline in total inflammatory facial lesion count will also be summarized by group and visit. Data will also be presented in graphics such as spaghetti plots.

11.4.3 Handling of missing values/censoring/discontinuations

All patients with available data after baseline and until Week 12 will be included in the interim and in the primary analyses. If study drug is permanently discontinued before Week 12, data collected after permanent discontinuation will not be considered for the purpose of the primary analyses. The primary variable analysis model is known to give unbiased results under the assumption that missing data are at random (MAR), i.e. given observed data the missingness does not depend on unobserved data. In the event that many patients discontinue treatment, alternative estimands considering the effect of LYS006 versus placebo may also be investigated. Further details will be provided in the Statistical Analysis Plan (SAP).

11.4.4 Sensitivity analyses

Commercially Confidential Information

11.5 Analysis of secondary variable(s)

11.5.1 Safety

For all safety analyses, the safety analysis set will be used if not otherwise specified. All listings and tables will be presented by treatment group.

Vital signs

All vital signs data will be listed by treatment group, subject, and visit/time and if ranges are available abnormalities (and relevant orthostatic changes) will be flagged. Summary statistics will be provided by treatment and visit/time.

ECG evaluations

All ECG data will be listed by treatment group, subject and visit/time, abnormalities will be flagged. Summary statistics will be provided by treatment and visit/time.

Clinical laboratory evaluations

For laboratory tests covered by the CTCAE version 4.0 or higher, the laboratory data will be graded accordingly. The calculation of CTCAE grades will be based on the observed laboratory values only, clinical assessments will not be taken into account. For laboratory tests covered by CTCAE, a Grade 0 will be assigned for all non-missing values not graded as 1 or higher. Grade 5 will not be used.

For laboratory tests where grades are not defined by CTCAE, results will be graded by the low/normal/high classifications based on laboratory normal ranges.

The following by-treatment summaries will be generated separately for hematology, biochemistry and urinary laboratory tests:

- frequency table for newly occurring on-treatment grades 3 or 4
- shift tables using CTCAE grades to compare baseline to the worst on-treatment value
- for laboratory tests where CTCAE grades are not defined, shift tables using the low/normal/high/(low and high) classification to compare baseline to the worst on-treatment value.
- listing of all laboratory data with values flagged to show the corresponding CTCAE grades and the classifications relative to the laboratory normal ranges.

Adverse events (AEs)

All information obtained on AEs will be displayed by treatment group and subject.

Summary tables for AEs include only AEs that started or worsened after first dose, the *treatment-emergent* AEs (TEAEs). However, all safety data (including those from the pre and post-treatment periods) will be listed and those collected during the pre-treatment and post-treatment period are to be flagged. Listings of all AEs will be provided.

The incidence of TEAEs (new or worsening after first dose) will be summarized by system organ class or preferred term, severity and by treatment group.

Deaths reportable as SAEs and non-fatal SAEs will be listed by patient and tabulated by type of AE and treatment group.

SAEs, non-serious AEs and AEs of special interest CCI will be tabulated.

A subject with multiple AEs within a body system is only counted once towards the total of this body system.

Study drug compliance assessment

Study drug compliance will be assessed by summarizing the duration of exposure, the actual total doses, frequency of dose interruption, and actual and relative dose intensities. Reason for dose interruption will be listed by patient and summarized.

Other safety evaluations

Commercially Confidential Information

Pregnancy test results will be listed by treatment group, subject and visit/time.

11.5.2 Other assessments

Not applicable.

11.6 Analysis of exploratory variables

Details of statistical methodologies for exploratory variables will be described in the SAP. Graphical presentation of the data will be performed where applicable.

11.6.1 Clinical Outcome Assessments

Facial inflammatory lesion count over time

Total inflammatory facial lesion count data over time will be visualized via individual profile plots for all subjects, where group allocation and responder status at Week 12 will be indicated. Individual facial inflammatory lesion counts (papules, pustules and nodules) over time will be summarized by lesion type, treatment group and visit/time and also be visualized by spaghetti plots and group summary plots. Estimates of the treatment effect over time will be taken from a MMRM model as described for the primary variable.

11.6.5 Exploratory biomarkers

Commercially Confidential Information

11.7 Sample size calculation

In total approximately 56 subjects are to be randomized with a 3:1:3 ratio to LYS006 high dose, low dose and placebo group. This should provide complete 12-week data of approximately 20 patients in the LYS006 high dose and placebo groups, with the assumption of around 20% dropout rate.

The table below shows the cumulative operating characteristics of the trial for the primary endpoint (LYS006 high dose versus placebo) at the interim analysis (IA), when approximately 15 patients in the LYS006 high dose group and 15 patients in the placebo group have completed 12 weeks (at about 75% enrolment); and at the final analysis when all patients have completed 12 weeks. The operating characteristics are presented with the probabilities to declare preliminary efficacy at IA and final analysis under different true difference in lesion counts between treatment groups (active-placebo/placebo).

With the log-normal assumption and a median of 20 lesions in the placebo group at Week 12, the 25% effect (active minus placebo being -0.288 on the log scale) corresponds to approximately 5 lesions difference in the median, which is considered the targeted difference from placebo (Section 11.4.2). If the true effect is 35% over placebo (active minus placebo

Novartis	Confidential	Page 103
Amended Protocol Version v06 (Clean)		Protocol No. CLYS006X2201

being -0.431 on the log scale), the probability of meeting the efficacy criteria is 87%, with 20 subjects from either LYS006 high dose group or placebo group. Effect of 35% corresponds to approximately 7 lesions difference in median, assuming a median of 20 lesions in the placebo group at week 12. If the true effect over placebo is 0, there is approximately 5% chance of declaring efficacy.

Table 11-1	Operating characteristics of decision rules
------------	---

	15:15 (IA)	20:20 (final analysis)
Sample size*	Chance of meeting both efficacy criteria	Chance of meeting both efficacy criteria
True effect = 0	5%	5%
True effect = 35%	80%	87%

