10.4 Data Monitoring Committee

In this proof-of-concept study, there is no a priori information as per the FDA Guidance of "situations in which safety concerns may be unusually high" or the patient population being studied is "potentially fragile population such as children, pregnant women or the very elderly, or other vulnerable populations, such as those who are terminally ill or of diminished mental capacity." Thus, an independent data monitoring committee will not be constituted.

The Novartis clinical team will review the safety data on a regular basis. A preliminary review of the safety data and assessment of efficacy, based on the calculated Bayesian probability of success will be performed at the first interim analysis by the Novartis clinical trial team and the overall recommendations on study continuation shared with the investigators. A re-assessment of the sample size based on the observed coefficient of variation in the primary endpoint between patients may also be performed.

At the time of the first interim analysis, the inflammatory facial lesion counts performed by the investigator will be used to compare the CCI high dose group with the placebo group. A Bayesian analysis will be performed to estimate the probability of success of the trial given the current data.

It is envisioned that the team may make three types of recommendations at the first interim analysis, namely:

- No safety or efficacy issues, ethical to continue the study as planned,
- Substantial coefficient of variation between patients in the primary endpoint requiring reassessment of the sample size,
- Serious safety concerns precluding further treatment in the study, regardless of efficacy.

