6.1.3 Statistical model, assumptions and hypotheses

Data up to Week 12 will be included in a Bayesian mixed effect model for repeated measures (MMRM) for the comparison of LYS006 high dose group versus placebo group at 12 weeks, which is of primary interest. Data from the LYS006 low dose group will also be included in this primary model at the time of IA and later analyses, but will mainly be summarized as described in the descriptive analyses section above.

The natural log transformed inflammatory facial lesion count is expected to be approximately normally distributed. It will be analyzed using a Bayesian mixed effect model for repeated measures (MMRM) using Proc MCMC in SAS software ([Chen 2011](#)). Baseline adjustment will be implemented by including the log transformed baseline inflammatory facial lesion count in the model as a continuous covariate. The model will also include treatment group, visit, treatment group by visit interaction, log transformed baseline inflammatory facial lesion count

Commercially Confidential Information

as fixed effects. Non-informative priors will be utilized for the fixed effects and for the covariance coming from a normal distribution and an inverse Wishart distribution, respectively. An unstructured covariance will be assumed; other covariance structures will be investigated if there is a convergence issue. The log transformed baseline inflammatory facial lesion count will be centered and standardized prior to being included in the model.

Bayesian posterior probabilities will be used to assess the following proof-of-concept (PoC) criteria as a guidance for decision making ([Fisch et al 2015](#)), though other criteria may be taken into account:

Efficacy criteria (only for primary objective) at IA and at the final analysis:

- If there is at least 90% probability that the treatment effect of LYS006 at 12 weeks is better than placebo, i.e., $\text{Prob}(y_{\text{LYS006}} - y_{\text{placebo}} < 0) > 90\%$, and
- If there is at least 50% probability that the treatment effect at 12 weeks is at least 25% in favor of LYS006, i.e., $\text{Prob}(y_{\text{LYS006}} - y_{\text{placebo}} < -0.288) > 50\%$.

Where y is the log transformed facial inflammatory lesion count.

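### Are the 87% success probability and 5% false-positive rate in Protocol 11.7 wrong for a final analysis with 20 patients per arm?

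*Protocol*

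**What the plan says.** Protocol 11.4.2 and SAP 6.1.3 set two criteria for the high-dose versus placebo comparison at Week 12 on the log lesion count. The first is "If there is at least 90% probability that the treatment effect of LYS006 at 12 weeks is better than placebo"; the second is "If there is at least 50% probability that the treatment effect at 12 weeks is at least 25% in favor of LYS006", that is, a log difference below -0.288. Protocol 11.4.2 applies both at two looks: "Efficacy criteria (only for primary objective) at IA and at the final analysis". On priors it states: "Non-informative priors will be utilized for the fixed effects and for the covariance".

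Protocol 11.7 then introduces Table 11-1: "The table below shows the cumulative operating characteristics of the trial for the primary endpoint". It places the interim at about 15 completers per arm and the final analysis at about 20 per arm, and describes the entries as chances of declaring preliminary efficacy at the interim and at the end. The entries are 5% and 80% in the 15:15 column, and 5% and 87% in the 20:20 column, for true effects of 0 and 35% (log difference -0.431). The text adds that with a 35% effect "the probability of meeting the efficacy criteria is 87%, with 20 subjects from either LYS006 high dose group or placebo group" and that "If the true effect over placebo is 0, there is approximately 5% chance of declaring efficacy".

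Protocol 10.4 describes what may come out of the interim: "It is envisioned that the team may make three types of recommendations at the first interim analysis". The three are to continue, to reassess the sample size, or to raise serious safety concerns.

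**The concern.** The sentence with the 87% ties it to 20 patients per arm, and the matching column is headed as the final analysis. A reader who skips the lead-in will take 87% and 5% as properties of one analysis of 20 versus 20. That cannot be right: with a fixed cut-off of -0.288, the chance of passing under no effect must fall as the sample grows from 15 to 20 per arm, yet both columns show 5%.

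An either-look figure also counts trials that pass at the interim and then miss the criteria at the end. Protocol 10.4 lists no efficacy declaration among its interim recommendations. If the go/no-go decision rests on the final data alone, the team would believe it has 87% power and a 5% false-go rate when it has about 83% and under 3%. The table also gives no row for the 25% effect that 11.7 names as the target.

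**Working it through.** **Inputs.** Criteria, prior type and the threshold -0.288 = ln 0.75 come from Protocol 11.4.2 and SAP 6.1.3. The alternative -0.431 = ln 0.65, the 15 and 20 per arm, and the four table entries come from Protocol 11.7. The SD of the log count (s) is not in the public text. It is an assumption, back-solved from Table 11-1.

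**Pass rule.** With a flat prior and a normal approximation, the posterior is centred on the estimate with spread SE = s × √(2/n). Criterion 1 needs an estimate below -1.2816 × SE; criterion 2 needs an estimate below -0.288. So a look passes when the estimate is below -max(0.288, 1.2816 × SE).

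**Which criterion binds.** At s = 0.47:
- n = 15: SE = 0.47 × √(2/15) = 0.1716, and 1.2816 × SE = 0.220.
- n = 20: SE = 0.47 × √(2/20) = 0.1486, and 1.2816 × SE = 0.190.

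Both lie below 0.288, so criterion 2 alone decides at either look.

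**Single looks.** Success at a 35% effect is Φ((0.431 - 0.288)/SE); the null pass rate is Φ(-0.288/SE).
- n = 15: Φ(0.833) = 79.8%; Φ(-1.678) = 4.7%.
- n = 20: Φ(0.962) = 83.2%; Φ(-1.938) = 2.6%.

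**Either look.** The two estimates have correlation √(15/20) = 0.866. P(either) = P(interim) + P(final) - P(both), with P(both) from the bivariate normal. This gives 87.2% at a 35% effect and 5.4% under the null.

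| | Table 11-1 | Single look, s = 0.47 | Cumulative, s = 0.47 |
|---|---|---|---|
| 15:15, effect 0 | 5% | 4.7% | 4.7% |
| 15:15, effect 35% | 80% | 79.8% | 79.8% |
| 20:20, effect 0 | 5% | 2.6% | 5.4% |
| 20:20, effect 35% | 87% | 83.2% | 87.2% |

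The cumulative column rounds to the plan's figures in every cell, and SDs from about 0.465 to 0.472 do the same. A simulation with estimated variance (400,000 trials) at s = 0.47 gave 79.7% and 4.6% at the interim, 83.1% and 2.7% at the final look, and 87.1% and 5.4% at either look.

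**Can the 20:20 column be a single look?** No SD allows it.
- A final-look success of 87% needs s of about 0.401. The final null rate is then 1.2%, and the interim figures are 83.5% and 2.5%.
- A final-look null rate of 5% needs s of about 0.554. The final success is then 79.3%, and the interim figures are 76.0% and 7.7%.

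**Interim passes later overturned.** At s = 0.47 these are 87.2 - 83.2 = 4.0 points at a 35% effect and 5.4 - 2.6 = 2.8 points under the null.

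**The 25% effect.** The true difference then equals the cut-off, so a single look passes with probability Φ(0) = 50% while criterion 2 binds. At either look it is 1 - (1/4 + arcsin(0.866)/(2π)) = 1 - (0.250 + 0.167) = 58%.

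**The case for a change.** The best case for a change is that one word in a lead-in is weak protection. The 87% sentence, the column header and the cell label all point to one analysis at 20 per arm, and no final-only figure is given. Cumulative figures describe the trial only if an interim pass stands. Protocol 10.4 names no efficacy outcome at the interim, while the criteria are applied again at the end. Under the null, 2.8 of the 5.4 points, just over half, are interim passes that the final data reverse. Nor can a reader see from the table that the targeted 25% effect passes a single look only half the time.

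The arithmetic stands; the inference that the plan is in error does not. Protocol 10.4 says what the team may recommend and also provides for an efficacy assessment at the interim, so it does not show that an interim pass is void. Protocol 11.4.2 applies the efficacy criteria at that look, and 11.7 speaks of declaring preliminary efficacy there. The sections that would state the interim rules (Protocol 3.6 and 11.9, SAP section 3) are redacted or not shown in the public versions, so a missing rule cannot be asserted.

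Replacing 5% by about 2.5% as the headline would understate the chance of meeting the criteria at some look when the drug does nothing. The 50% pass rate at a 25% effect follows directly from how criterion 2 is written; a row for it would be convenient, but its absence hides nothing.

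**Conclusion.** The concern does not call for a change. The 87% and 5% in Protocol 11.7 are correct as the cumulative figures that the lead-in announces, and one SD reproduces the whole of Table 11-1 on that reading. What is left is a labelling weakness: the 87% sentence and the 20:20 header do not repeat that an interim pass counts.

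For a reader who wants the final look alone, the values are about 83% at a 35% effect (82.9% to 83.4%) and 2.5% to 2.8% under no effect. They rest on an SD of 0.465 to 0.475 back-solved from the table, a flat prior, a normal approximation and completers only; the planned repeated-measures model also uses partial data. The sponsor's own SD would be needed to print exact figures.

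The difference is about 4 points of success probability, and the false-go rate at the final look is lower than quoted. The trial is a non-confirmatory proof of concept in which the criteria guide the decision alongside other considerations. Relabelling the column would leave sample size, thresholds, analysis and conclusion as they are.

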11.8 Power for analysis of key secondary variables

Not Applicable.

11.9 Interim analyses

12 Ethical considerations

12.1 Regulatory and ethical compliance

This clinical study was designed and shall be implemented, executed and reported in accordance with the ICH Harmonized Tripartite Guidelines for Good Clinical Practice, with applicable local regulations (including European Directive 2001/20/EC, US Code of Federal Regulations Title 21, and Japanese Ministry of Health, Labor, and Welfare), and with the ethical principles laid down in the Declaration of Helsinki.

12.2 Responsibilities of the investigator and IRB/IEC

Before initiating a trial, the investigator/institution must obtain approval/favorable opinion from the Institutional Review Board/Independent Ethics Committee (IRB/IEC) for the trial protocol, written informed consent form, consent form updates, subject recruitment procedures (e.g. advertisements) and any other written information to be provided to subjects. Prior to study start, the investigator is required to sign a protocol signature page confirming his/her agreement to conduct the study in accordance with these documents and all of the instructions and procedures found in this protocol and to give access to all relevant data and records to Novartis monitors, auditors, Novartis Quality Assurance representatives, designated agents of Novartis, IRBs/IECs, and regulatory authorities as required. If an inspection of the clinical site is requested by a regulatory authority, the investigator must inform Novartis immediately that this request has been made.

For multi-center trials, a Coordinating Investigator will be selected by Novartis by the time of Last Patient Last Visit to be a reviewer and signatory for the clinical study report.

